## 10.3 POPULATIONS FOR ANALYSES

### 10.3.1 Evaluable for toxicity

All participants will be evaluable for toxicity from the time of their first treatment with KPT-8602.

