## 3 STUDY IMPLEMENTATION

### 3.1 STUDY DESIGN

The study consists of two phases:

- Phase I: Safety evaluation with determination of the recommended phase 2 dose (RP2D) of KPT-8602 in combination with Inqovi, and
- Phase II: Efficacy evaluation of KPT-8602 in combination with Inqovi

Participants will be enrolled into one of two cohorts, depending on the phase of study as follows:

- Phase I:
  - **Cohort 1:** Participants with higher-risk MDS that will be treated with Inqovi for 5 days, followed by KPT-8602 at escalating doses.
- Phase II:
  - **Cohort 2:** Participants with higher-risk MDS that will be treated with Inqovi for 5 days, followed by KPT-8602 at the RP2D.

In Phase I, participants enrolled in Cohort 1 will be treated with Inqovi 35 mg/100 mg daily on Days 1-5 of each 28-day cycle, plus KPT-8602 at the corresponding dose level and schedule..

Dose-escalation will follow a standard 3+3 design (see Section [3.1.2](#)), with DLT assessment during the first 28 days of treatment.

In Phase II, participants enrolled in Cohort 2 will be treated with Inqovi 35 mg/100 mg daily on Days 1-5 of each 28-day cycle, plus KPT-8602 at the RP2D identified in Phase I.

The study drugs will be self-administered by the patient, except on days of PK blood draws.

Participants in Cohorts 1 and 2 are eligible to participate in the study if they have received a minimum of 4 cycles of HMA therapy with inadequate response (failure to achieve at least a PR, or experienced disease progression prior to completing 4 cycles). For participants on HMA therapy with Inqovi prior to enrollment, descriptions of initiation of study therapy refer to initiation of KPT-8602 only. Of note, participants receiving Inqovi prior to enrollment must be on the standard dose (35 mg decitabine and 100 mg cedazuridine) without prior dose-reductions.

In both Phase I and Phase II, participants will continue treatment until disease progression, death, unacceptable toxicities as listed in Section [3.3.2](#), or another off-treatment criterion is met (see Section [3.7.1](#)) as long as no other contraindications to further treatment. Participants that do not achieve at least partial remission following cycle 6 will not receive additional treatment.

Blood samples for correlative research will be collected (Section [5.1](#)). Participants may be admitted on day 8 of cycle 1 for pharmacokinetics (PK) studies to be performed, and on other days if necessary or for convenience.

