## Phase I/II Study Schema

### 3.1.1 Dose Limiting Toxicity (DLT)

The DLT evaluation window will be the first 28 days of study treatment. No dose reductions or interruptions are allowed during the DLT observation period.

A DLT is defined as any of the following treatment-related toxicities (based on CTCAE Version 5.0):

- Any Grade 5 toxicity, unless due to underlying disease, disease progression, or accidental injury.
- Any Grade  $\geq 3$  non-hematologic toxicity, except:
  - Grade 3 or 4 isolated electrolyte abnormalities that resolve, with or without intervention, to Grade  $\leq 2$  within 72 hours
  - Grade 3 nausea, vomiting, or diarrhea that does not require/prolong hospitalization, does not require TPN or NGT feeding, and resolves to Grade  $\leq 2$  within 72 hours
  - Grade 3 fatigue, fever, flu-like symptoms, or headache lasting  $\leq 72$  hours
  - Grade 3 laboratory abnormalities that are not associated with organ pathology
  - Direct complications of cytopenia(s) due to active myeloid malignancy, such as:
    - Grade 3 or 4 febrile neutropenia
    - Grade 3 or 4 infection
    - Grade 3 or 4 hypotension explained by sepsis
    - Grade 3 or 4 hemorrhage/bleeding
- Confirmed Hy's law cases, defined as:
  - AT (ALT or AST) elevation  $> 3$  times upper limit of normal (ULN), AND
  - Total bilirubin  $> 2$  times ULN, without initial findings of cholestasis (elevated serum alkaline phosphatase), AND

- No other immediately apparent possible causes of AT elevation and hyperbilirubinemia, including, but not limited to, viral hepatitis, pre-existing chronic or acute liver disease, or the administration of other drug(s) known to be hepatotoxic.
- In the absence of active MDS, hematologic DLTs for each arm include:
  - any Grade  $\geq 4$  decrease ANC or PLTs lasting more than 28 days.
- Any adverse reaction that leads to dose reduction or withdrawal of KPT-8602.

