#### **3.2.2 Decitabine and Cedazuridine (Inqovi)**

In both Phase I and Phase II, the study drug of KPT-8602 will be given in combination with standard-of-care (SOC) FDA-approved PO decitabine and cedazuridine (Inqovi).

- Inqovi will be administered via oral route once daily on Days 1-5 of each treatment cycle, according to guidelines outlined in the FDA product label.

The tablet should be taken on an empty stomach, 2 hours before or 2 hours after meals, and at the same time each day.

Tablet should be swallowed whole, and may not be crushed, cut, or chewed.

Participants will be asked to complete a medication diary. If a dose is missed within 12 hours of the time it is usually administered, administer the missed dose as soon as possible and then resume the normal daily dosing schedule. Extend the dosing period by 1 day for every missed dose to complete 5 daily doses for each cycle. If a dose is vomited, do not administer an additional dose (continue with the next scheduled dose).

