## 6 DATA COLLECTION AND EVALUATION

### 6.1 DATA COLLECTION

The PI will be responsible for overseeing entry of data into a 21 CFR Part 11-compliant data capture system provided by the NCI CCR and ensuring data accuracy, consistency and timeliness. Data entry may also be achieved via other systems as permitted by CCR requirements (e.g., Labmatrix, PROs directly via Scribe). The principal investigator, associate investigators/research nurses and/or a contracted data manager will assist with the data management efforts. Primary and final analyzed data will have identifiers so that research data can be attributed to an individual human subject participant.

All adverse events, including clinically significant abnormal findings on laboratory evaluations, regardless of severity, will be followed until resolution or stabilization of event.

Document AEs from the first study intervention, study day 1, through 30 days after the last dose of any study drug. Beyond 30 days, only adverse events which are serious and related to the study investigational agent need to be recorded.

An abnormal laboratory value will be recorded in the database as an AE **only** if the laboratory abnormality is characterized by any of the following:

- Results in discontinuation from the study
- Is associated with clinical signs or symptoms
- Requires treatment or any other therapeutic intervention
- Is associated with death or another serious adverse event, including hospitalization.
- Is judged by the Investigator to be of significant clinical impact
- If any abnormal laboratory result is considered clinically significant, the investigator will provide details about the action taken with respect to the test drug and about the participant's outcome.

The PI (or designee) evaluation of each AE not captured in the clinical database determining that it meets the criteria above will be documented in the source documents. **Note:** The investigator performing the assessment must be a licensed provider listed on the 1572.

**End of study procedures:** Data will be stored according to HHS, FDA regulations, and NIH Intramural Records Retention Schedule as applicable.

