## 10 STATISTICAL CONSIDERATIONS

### 10.1 OBJECTIVES AND ENDPOINTS

OBJECTIVES	ENDPOINTS	JUSTIFICATION FOR ENDPOINTS
Primary		
Phase I: To determine the recommended phase 2 dose (RP2D) of KPT-8602 in combination with Inqovi in adult participants with higher-MDS	- Recommended phase 2 dose (RP2D), as determined by the number of participants with DLTs reported at each dose level studied (Section 3.1.1 ) -Any toxicities identified from Day 1 of study drug through 28 days after the first dose. AEs are reported by type and grade. -ORR (defined as CR+PR+mCR with HI) per each cohort Responses will be assessed after every cycle with CBC and at the end of Cycles 2 and 6 with bone marrow assessment during treatment and every 3-6 months after that until time of disease relapse, disease progression, or death, or 8 years, whichever occurs first.	Standard endpoint for Phase I protocol Efficacy evaluation, standard for Phase II protocol
Secondary		
Phase I: To characterize the PK properties of KPT-8602 in combination with Inqovi in MDS participants	-AUC, half-life, and steady state concentration, measured by the KPT-8602 blood concentration 1, 2, 3, 4, 8, 24 and 48 hours after the product administration on days 8 and 21 of cycle one	PK studies to evaluate for adequate absorption of therapy and further define half-life/AUC and other properties of the study drug, when given in combination with Inqovi
Phase II: To further evaluate the PK properties and safety of KPT-8602 in combination with Inqovi in MDS participants	-Safety, as measured by: Incidence of AEs, SAEs; and AEs leading to discontinuation, death, and laboratory abnormalities, assessed at least weekly through cycle 3 and then at the start and every cycle after that	Confirm safety of the study drug at the RP2D
Exploratory		
To evaluate the relationship between KPT-8602 exposure (PK) and response	Each of these will be evaluated using descriptive methods and reported as exploratory results. If any statistical	Evaluate mechanism of the study drug, target engagement,

OBJECTIVES	ENDPOINTS	JUSTIFICATION FOR ENDPOINTS

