## 10.2 STATISTICAL HYPOTHESIS AND SAMPLE SIZE DETERMINATION

The trial will begin with a phase I dose-escalation phase using a standard 3+3 design which will enroll participants with relapsed/refractory HR-MDS. Up to 18 participants may be enrolled based on the 3+3 design.

Participants will be eligible for the DLT evaluation if  $\geq 90\%$  (9 out of 10 doses) of KPT-8602 and  $\geq 80\%$  (4 out of 5 doses) of Inqovi were taken within the DLT period. Participants not evaluable for toxicity, will be replaced in the dose level.

Phase II will use a Simon's minimal two-stage design, applied separately as noted below:

- Trial will be conducted using a Simon minimax two-stage phase II trial design to rule out an unacceptably low response rate of 25% ( $p_0=0.25$ ) in favor of an improved response rate of 45% ( $p_1=0.45$ ) in order to determine if the combination of KPT-8602 with Inqovi will be able to improve upon an expected 30-40% response rate in participants who have received other agents. With two-sided alpha=0.05 and beta=0.20, the first stage will enroll 21 evaluable participants, and if 0 to 5 of the 21 have a response, then no further participants will be accrued. If 6 or more of the first 21 participants have a response, then accrual would continue until a total of 43 evaluable participants have been treated. If there are only 6-16 participants with a response out of 43 participants, this would be an uninterestingly low response rate. If there were 17 or more of 43 (39.5%) who experienced a response, treatment would be sufficiently interesting to warrant further study in later trials. The probability of early termination under the null (25%) response rate is 56.7%.

It is expected that up to 12-15 participants with MDS may be accrued per year. Thus, in order to accrue up to  $18 + 43 = 61$  participants (which may be reduced by up to 6 if up to 6 participants in phase I may be included in phase II), and to allow for a small number of inevaluable participants (12), it is expected that 3-4 years may be required to accrue the required 73 participants. Note: To allow for screen failures (7), the accrual ceiling will be set at 80 participants for the purposes of the NIH accrual ceiling.

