## **17.11 APPENDIX K: PARTICIPANT MEDICATION DIARY**

Cohort 1 and 2 – Medication Diary

Cycle: \_\_\_\_\_ Participant's ID: \_\_\_\_\_

Instructions:

1. Complete one form for each cycle of treatment.
2. You will take Inqovi once daily on Days 1-5 or Days 1-4, Days 1-3 or Day 1, 3 and 5 depending on the dose level you are assigned,
3. The tablet should be taken on an empty stomach, 2 hours before or 2 hours after meals, and at the same time each day.
4. If a dose of Inqovi is missed within 12 hours of the time it was supposed to be taken, it should be taken as soon as possible. If it is past 12 hours, the dose should not be made up. Extend the dosing period by 1 day for every missed dose to complete the total number of daily doses for each cycle.
5. You will take KPT-8602 once daily on Days 8-12 for all dose levels, and possibly on Days 13-21 or on Days 15-19 depending on the dose level you are assigned, during a 28-day cycle.
6. If a dose of KPT-8602 is missed within 12 hours of the time it was supposed to be taken, it should be taken as soon as possible. If it is past 12 hours, the dose should not be made up. Extend the dosing period by 1 day for every missed dose to complete the total number of daily doses for each cycle.
7. If you vomit after taking a dose of KPT-8602 and/or Inqovi, do not retake the dose. Take the next dose of KPT-8602 and/or Inqovi at the regular schedule.
8. If you miss any doses please contact us.
9. Record the date, the number of tablets that you took, and when you took them. If you miss a dose, please record this also below.
10. If you have any comments or notice any side effects, please record them in the 'comments' column.
11. On the days you are being seen in clinic, you must bring in your medication supply from home; however, you should not take your medication until instructed, as the blood draws must be timed with when you take your medication.
12. Please bring this form and your bottles (even it is empty) when you come for your clinic visits.

Day	Date	Study Drug				Comments	
		KPT-8602		INQOVI			
		Time	# of Tablets	Time	# of Tablets		
1		None	None				
2		None	None				
3		None	None				
4		None	None				

Day	Date	Study Drug				Comments	
		KPT-8602		INQOVI			
		Time	# of Tablets	Time	# of Tablets		
5		None	None				
6		None	None	None	None		
7		None	None	None	None		
8				None	None		
9				None	None		
10				None	None		
11				None	None		
12				None	None		
13				None	None		
14				None	None		
15				None	None		
16				None	None		

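### Section 10.3.1 starts toxicity evaluability at the first KPT-8602 dose (Cycle 1 Day 8), although protocol Inqovi starts on Day 1 and other sections count events from Day 1

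*Combined protocol and SAP*

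**What the plan says.** - Section 10.3.1, the only definition of the toxicity population: "All participants will be evaluable for toxicity from the time of their first treatment with KPT-8602".
- Section 3.2.2: "Inqovi will be administered via oral route once daily on Days 1-5 of each treatment cycle". The study calendar footnotes apply this to both cohorts.
- Appendix K: "You will take KPT-8602 once daily on Days 8-12 for all dose levels". The dose tables in Sections 3.1.2 and 3.3.1 agree that Day 8 is the first KPT-8602 day at all four levels.
- Section 6.1: "Document AEs from the first study intervention, study day 1, through 30 days after the last dose of any study drug".
- Section 10.1, Phase I toxicity endpoint: "Any toxicities identified from Day 1 of study drug through 28 days after the first dose".
- Section 3.1.1: "The DLT evaluation window will be the first 28 days of study treatment". Section 10.2 makes DLT evaluability depend in part on whether "4 out of 5 doses) of Inqovi were taken within the DLT period".
- Section 3.1: "For participants on HMA therapy with Inqovi prior to enrollment, descriptions of initiation of study therapy refer to initiation of KPT-8602 only".
- Section 8.3 starts SAE reporting to the sponsor at the first administration of investigational product and does not say whether that means Inqovi or KPT-8602.

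**The concern.** The regimen under test is the combination, and its first component is given a week before the second. The plan collects events from Day 1, but its one analysis-population statement starts the clock on Day 8. Collecting an event does not decide whether it is analysed, and no section brings Day 1-7 events, or participants who never take KPT-8602, back into the toxicity set.

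The Phase II secondary objective includes the safety of KPT-8602 with Inqovi, and Section 14.2.2 itself warns of fatal and serious myelosuppression and infection with Inqovi. A participant who dies or stops in the first week because of toxicity would, on the literal wording, leave both numerator and denominator for a reason linked to the outcome. That would lower the reported rates of early death, infection and discontinuation.

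**Working it through.** **1. Where each clock starts**

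| Section | Subject | Start |
|---|---|---|
| 6.1 | AE recording | Study day 1, first study intervention |
| 10.1 | Phase I toxicity endpoint | Day 1 of study drug |
| 3.1.1, 3.1.2, 10.2 | DLT period | First 28 days, described in 3.1.2 as the first cycle, with Inqovi doses counted in it |
| 10.3.1 | Toxicity evaluability | First KPT-8602 dose, Day 8 |
| 8.3 | SAE reporting | First investigational product, drug not specified |

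Because 3.1.2 describes the DLT period as the first cycle, the five Inqovi doses counted in it are those of Cycle 1 Days 1-5. This, with 6.1, fixes Day 1 as Cycle 1 Day 1.

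**2. What 10.3.1 does, taken literally**

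- Event on Days 1-7, participant goes on to KPT-8602: in the denominator, but the event precedes evaluability.
- Stops or dies before Day 8: never evaluable, so lost from numerator and denominator.
- Event on or after Day 8, including Inqovi days in later cycles: unaffected.

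The gap is therefore Cycle 1 Days 1-7: 7/28 = 25% of the cycle's calendar days, containing all five Cycle 1 Inqovi doses. This is a share of time, not of risk.

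**3. Phase I or Phase II**

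A Phase I participant who stops before Day 8 has taken 0 of 10 KPT-8602 doses, below the 9 of 10 that Section 3.1.2 requires, and is replaced whatever 10.3.1 says. The dose decision therefore does not depend on 10.3.1 for these participants. The effect is on descriptive safety tables, mainly in Phase II.

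**4. Size**

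The documents give no rate of loss before Day 8, so the following is assumed. Suppose 43 Phase II participants reach KPT-8602 and none dies later, and k more die before Day 8. The literal rule reports 0/43; counting everyone treated gives k/(43 + k):

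- k = 0: 0/43, no difference
- k = 1: 1/44 = 2.3%
- k = 2: 2/45 = 4.4%
- k = 3: 3/46 = 6.5%

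The k participants are added to 43 because Section 10.2 counts 43 response-evaluable participants. Section 10.3.2 normally requires one cycle of therapy and a re-evaluation for that status, except for objective progression before the end of Cycle 1. Someone who dies before Day 8 without documented progression would fall in the separate allowance of 12 inevaluable participants.

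**5. The plan's own safety figures**

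The Phase II pause boundaries in Section 10.4.4.1 take the smallest x with P(p > 0.2 | Beta(1 + x, 1 + n - x)) > 0.80, from n = 9. Recomputing gives 3/9, 4/11, 5/15, 6/20, 7/24, 8/28 and 9/32, exactly as stated (posterior at 3/9: 0.879). The fix does not change them.

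**The case against.** The strongest defence is Section 3.1: for participants already on Inqovi, starting study therapy means starting KPT-8602. Eligibility describes prior therapy by the Inqovi tablet dose, so such participants are expected and may be numerous. Section 3.2.2 once calls KPT-8602 the study drug given with standard-of-care Inqovi, and Sections 10.4.3 and 10.4.4 report toxicity by dose level of the agent. Before Day 8 of Cycle 1 no combination has been given, so starting at the added agent could be a deliberate choice.

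This explains the wording but does not remove the inconsistency. The Section 3.1 sentence covers only participants already on Inqovi, and the washout rule in 2.1.1.8 implies that other prior HMAs are possible. Sections 3.1, 3.3 and 6.1 also use study drug for either agent. If the term is ambiguous, it needs settling anyway.

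A second defence is that nothing goes unseen: AEs are recorded from Day 1, the team reviews participants weekly (7.4.1), and deaths within 30 days of a research intervention that are not due to progression are reported (7.3). That is correct for oversight, but none of these sections defines an analysis set.

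Two parts of the defence stand in full. A reader might infer that 10.1 defines a safety set from Day 1. It gives only a Phase I endpoint window, and the Phase II safety endpoint has no start day. A reader might also infer that the plan removes early deaths from its tables. Section 10.3.1 speaks of all participants and then gives a start time, and no section orders such removal. The exclusion follows from a literal reading and is not a demonstrated bias.

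**Conclusion.** The inconsistency is real and should be corrected before the safety analysis. The sole toxicity-population statement starts a week later than AE recording, the Phase I toxicity endpoint and the DLT period. Followed literally, it can understate early toxicity of the combination. The size is unknown and probably small: nothing if no one has an event or stops before Day 8, and 0/43 against 2/45 (4.4%) under the assumed two early deaths.

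Two stronger conclusions are tempting but unsupported. One is that two early deaths would turn 2/43 into 0/41. That treats people who die before Day 8 as part of the response-evaluable 43, which Section 10.3.2 would normally not allow. The other is that the Phase II pause rule is weakened: if one of three DLTs in nine participants went uncounted, the posterior at 2/9 would be 0.678 and there would be no pause. Section 10.4.4.1, however, counts toxicities that meet the DLT definition, whose window is the first 28 days of study treatment, and it does not refer to 10.3.1. The share of DLTs arising before Day 8 is also not given.

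**What to change.** - Replace the 10.3.1 sentence with: *All participants who receive at least one on-protocol dose of either study drug are evaluable for toxicity from that first dose (Cycle 1 Day 1).*
- State that, for this purpose, the rule also applies to participants already on Inqovi before enrollment, notwithstanding the Section 3.1 sentence on initiation of study therapy. Otherwise the new text would conflict with 3.1.
- Align the start of SAE reporting in Section 8.3 with Section 6.1.
- If toxicity after KPT-8602 exposure is of separate interest, tabulate a KPT-8602-exposed subset as a secondary display.
- Leave the DLT-evaluability rule in 3.1.2 and 10.2 as a separate definition.

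The cost is a few sentences. AE collection, sample size and pause boundaries stay as they are. The downside is that reported toxicity may rise slightly and will include some events due to Inqovi alone, which the optional subset would help to separate.

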### 10.3.2 Evaluable for objective response

Only those participants who have measurable disease present at baseline, have received at least one cycle of therapy, and have had their disease re-evaluated will be considered evaluable for response. These participants will have their response classified according to the definitions stated below. (Note: Participants who exhibit objective disease progression prior to the end of cycle 1 will also be considered evaluable.)

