## 10.4 STATISTICAL ANALYSES

### 10.4.1 General Approach

- Participants in phase I will be evaluated for safety, reporting the toxicities noted per dose level.
- Participants in phase II will have their response rate reported along with a confidence interval.

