### 10.4.2 Analysis of the Primary Endpoints

- Participants enrolled in phase I will have the grades and types of toxicity reported at each dose level. The overall estimate of the fraction of participants who have a DLT at the RP2D will be reported.
- Participants evaluated in phase II will have the fraction with clinical responses reported, with a 95% confidence interval.

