#### 10.4.6 Planned Interim Analyses

As indicated above in Section **10.2**, participants in phase II will be evaluated after 21 participants have been treated, an evaluation will be performed of the responses at that point to determine suitability to enroll the remaining participants. Specifically, the trial will proceed to the second stage if there are least 6 responses out of 21 participants with HR-MDS with a safety follow-up through day 28 required for the interim analysis, enrollment to the cohort will be halted to allow for an analysis by the study investigator. A brief memo will be created by the study investigator to document the number of responses in the first stage and will be reviewed by the PI and study team. The memo will be provided to study sponsor prior to continuation of accrual. Also, if the required number of responses is observed before that time, the memo will be generated, reviewed and provided to the study sponsor at that point without a pause in accrual. Response rates will be calculated using the revised International Working Group (IWG) 2006 response criteria for all responses, except hematologic improvement (HI) responses which will use the IWG 2018 response criteria, as described in the protocol.

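### Phase II ORR is planned only among evaluable participants, so people lost in cycle 1 without progression are replaced rather than counted as non-responders, and no all-treated ORR is planned

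*Combined protocol and SAP*

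**What the plan says.** Section 10.3.2 sets three conditions for response evaluability: measurable disease at baseline, at least one cycle, and a re-evaluation. Participants must "have received at least one cycle of therapy, and have had their disease re-evaluated will be considered evaluable for response". There is one exception: "Participants who exhibit objective disease progression prior to the end of cycle 1 will also be considered evaluable". Death without progression, complete withdrawal and a missing re-evaluation are not mentioned.

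Section 10.2 counts in the same unit. For stage 1, "the first stage will enroll 21 evaluable participants"; if 6 or more respond, "then accrual would continue until a total of 43 evaluable participants have been treated". It allows for 12 inevaluable participants on top of the 61 needed for Phases I and II together.

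Other sections describe the group differently:

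- Section 10.4.1 has no restriction: "Participants in phase II will have their response rate reported along with a confidence interval".
- Section 10.4.2 reads: "Participants evaluated in phase II will have the fraction with clinical responses reported, with a 95% confidence interval".
- Section 10.4.6 reads: "participants in phase II will be evaluated after 21 participants have been treated".

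For safety the set is wider. Section 10.3.1 states: "All participants will be evaluable for toxicity from the time of their first treatment with KPT-8602". The response table in 6.3.1 classes death during treatment as Failure.

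**The concern.** Phase II is a single-arm go/no-go decision, so the denominator is part of the result. ORR is CR, PR or marrow CR with hematologic improvement (10.1), and a response must last at least 4 weeks (6.3.1). A person who dies or leaves treatment entirely in cycle 1, or is never reassessed, will for practical purposes have no documented response. Leaving such people out and enrolling others in their place can raise ORR or leave it unchanged.

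The plan foresees losses of this kind. Under 3.1.1, a related Grade 5 event and an adverse reaction leading to withdrawal of KPT-8602 are both DLTs, and the Phase II toxicity rule in 10.4.4.1 uses that definition. A participant who dies of a treatment-related cause in cycle 1 after starting KPT-8602 would count in the toxicity rule, yet appear in neither the numerator nor the denominator of ORR. The more early losses the combination causes, the further the evaluable ORR can drift from the rate among everyone treated.

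**Working it through.** **Inputs.** From 10.2: null rate 0.25; target rate 0.45; stop if 5 or fewer of 21 respond; success if 17 or more of 43 respond; two-sided alpha 0.05; power 0.80; stated early termination 56.7%. The Phase II exclusion share *d* is not in the documents, so 2%, 5% and 10% are assumed.

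**1. Reproduce the plan.** With X1 ~ Bin(21, p) and X2 ~ Bin(22, p):

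- P(early stop) = P(X1 ≤ 5)
- P(success) = Σ P(X1 = x) · P(X2 ≥ 17 − x), for x = 6 to 21

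At p = 0.25, early termination is 0.567 and P(success) is 0.0245. At p = 0.45, P(success) is 0.8005. The plan's figures hold, with 0.025 in the upper tail. The Simon arithmetic is sound; the issue is who is counted.

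**2. Size without any assumption about the 25%.** Suppose a boundary result is seen among evaluable participants and k treated people were excluded, none responding. The all-treated rate is then r/(n + k).

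| Look | k = 0 | k = 1 | k = 2 | k = 5 |
|---|---|---|---|---|
| Stage 1 minimum pass | 6/21 = 28.6% | 6/22 = 27.3% | 6/23 = 26.1% | not shown |
| Final minimum success | 17/43 = 39.5% | 17/44 = 38.6% | 17/45 = 37.8% | 17/48 = 35.4% |
| Exact 95% CI, final | 25.0 to 55.6 | 24.4 to 54.5 | 23.8 to 53.5 | 22.2 to 50.5 |

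Expected exclusions needed to reach 43 evaluable are 43/(1 − d) − 43, which gives 0.9, 2.3 and 4.8 at d = 2%, 5% and 10%.

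**3. Type I error under two readings of the 25%.** If 25% is the all-treated rate and excluded people do not respond, the rate among evaluable participants is 0.25/(1 − d). Putting that through the same rule:

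| d | Evaluable rate | P(early stop) | Type I error |
|---|---|---|---|
| 0 | 0.2500 | 0.567 | 0.0245 |
| 2% | 0.2551 | 0.545 | 0.030 |
| 5% | 0.2632 | 0.511 | 0.039 |
| 10% | 0.2778 | 0.450 | 0.062 |

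If 25% is the rate among evaluable participants, the first row applies whatever d is.

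**4. Power if the all-treated set were made primary.** If 45% was meant for evaluable participants and n stays 43, the all-treated rate under the alternative is 0.45(1 − d), that is 0.441, 0.4275 or 0.405. Power falls from 80.0% to 76.6%, 70.9% or 59.9%.

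**The case against.** The strongest reply is that 10.2 is consistent within itself. The 25%, the 45% and both counts stand in one paragraph expressed in evaluable participants, so the natural reading is that the rates refer to that group. This stands. A reader might infer that the design's type I error is inflated, but the documents do not support that as a general statement. It follows only if 25% is an all-treated rate, which the plan does not say.

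A reader might also infer that everyone who stops KPT-8602 in cycle 1 is dropped. The text does not go that far. Section 3.3 defines cycle number by calendar time and does not change it when one drug is held. It also lets a participant taken off one drug stay on the other if benefiting. Section 6.3 re-evaluates by CBC after each cycle. Someone who stops only KPT-8602 and continues Inqovi may therefore remain evaluable. Because at least one cycle is undefined, this cannot be settled. The firm cases are death or complete withdrawal in cycle 1 without progression, and no re-evaluation.

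Nor is an upward bias certain. It is nil if nobody is excluded, and a later response in someone who missed only the one-cycle condition is improbable but not impossible.

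The allowance of 12 inevaluable out of 73 (16.4%) invites use as an exclusion rate. It covers both phases and may include Phase I participants replaced because they were not evaluable for DLT, so it shows that losses are expected but does not estimate the Phase II share.

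The Bayesian toxicity rule partly meets the worry about early toxicity, because DLTs are monitored separately. It does not correct the ORR. The wording differences are a lesser matter: 10.4.6 refers back to 10.2, so *treated* there is probably shorthand, and *evaluated* in 10.4.2 is compatible with *evaluable*.

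**Conclusion.** The point holds as one about the analysis population and its reporting. Sections 10.2 and 10.3.2 together replace participants who die or withdraw completely in cycle 1 without progression, or who are never re-evaluated. No section restores them through an all-treated ORR or a rule for missing responses. The Failure label in 6.3.1 sits uneasily with this but does not repair it, because 10.3.2 classifies responses only for evaluable participants.

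Relative to all treated, the bias is upward or nil, taking excluded participants as non-responders. With 2 to 5 exclusions, a minimum success moves from 39.5% to between 37.8% and 35.4%. That is modest beside an interval of 25.0 to 55.6, but it bears on a decision taken at a fixed threshold. The type I figures of 0.030 to 0.062 rest on two assumptions, the exclusion share and an all-treated reading of the 25%. Without the second, the error stays 0.0245.

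**What to change.** In 10.4.2 and 10.4.6, report at both looks the ORR with exact 95% CI among all Phase II participants who received any on-study treatment. Count early death, withdrawal or no re-evaluation as non-response. Place it beside the evaluable ORR, with the number excluded and the reasons. Basing this set on any on-study treatment also captures anyone lost on Inqovi before the first KPT-8602 dose on Day 8, whom the toxicity set in 10.3.1 misses.

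In 10.3.2, define at least one cycle, including the case where one drug is stopped and the other continues. Use one term for the 21 and the 43 in 10.2, 10.4.2 and 10.4.6. State in 10.2 which population the 25% and 45% describe.

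The cost is wording, one extra line of analysis at each look, and possibly a slightly lower ORR on display. The Simon design is unchanged. Making the all-treated set primary is a further choice for the sponsor. If that is done with n = 43 and 45% was meant for evaluable participants, power must be restated (76.6%, 70.9% or 59.9% at 2%, 5% or 10% exclusion) or the design recomputed.
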